Title: Smoking Cessation Pilot for People Living With HIV (PLWH)

NCT Number: **NCT04808609**

Document Date: 6/1/2021

Stand Alone Protocol: SMOKING CESSATION PILOT – IRB-AAAS6990

PI: [name]

Background:

Of the approximately one million persons living with HIV (PLWH) in the United States (U.S.), it is estimated that between 40-70% smoke cigarettes, at least three times the prevalence (14%) observed in the general U.S. adult population. Consequently, PLWH experience substantial tobacco-related morbidity and mortality. In PLWH, after achieving and maintaining a suppressed viral load, smoking cessation is the next most important health behavior to maximize both quality of life and life expectancy. Indeed, PLWH who quit smoking upon entering HIV care gain greater than 5 years of life expectancy as compared to those who enter HIV care and continue smoking.

Given the high prevalence of cigarette smoking among PLWH and the benefit of smoking cessation, there is an urgent need for swift action to intervene to reduce tobacco use rates. However, evidence to improve tobacco cessation among PLWH is inadequate. Few tobacco cessation interventions have been tested among PLWH, and of those which have, there is 'very low' quality evidence that tobacco cessation interventions were effective in the short-term, and 'moderate' quality evidence indicating similar outcomes to controls in the long-term.₃ Given the few randomized controlled trials (RCTs) examining smoking cessation interventions for PLWH, and the major methodological limitations of many of these studies (e.g., lack of randomization, comparison conditions, treatment fidelity assessments, abstinence verification tests), it is critical to develop evidence-based tobacco cessation interventions to address the complex and unique needs of PLWH (e.g., risk factors, treatment needs). Tailored cessation studies designed for dissemination and implementation are necessary to focus efforts on PLWH who use tobacco products.

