Recruitment: We will recruit PLWH by posting flyers at local clinics and community-based organizations throughout New York City. Potential participants will be pre-screened for eligibility over the phone by study staff. We will also provide enrolled participants with a study flyer to share with potentially eligible individuals.

Study Populations: Our study participants will consist of 40 individuals who smoke tobacco. Inclusion criteria. (1) PLWH; (2) \geq 18 years of age; (3) own an Android smartphone; (4) understand and read English; (5) not pregnant or breastfeeding; (6) permanent contact information; (7) smokes \geq 5 cigarettes per day for the past 30 days; (8) interested in quitting smoking within 30 days; and (9) blow >5 CO into a breath analyzer at baseline. Exclusion criteria. (1) self-report being HIV-negative or unknown status; (2) pregnant, breastfeeding, or planning to become pregnant during the study period; (3) planning to move within 3 months of enrollment; (4) a positive history of a medical condition that precludes use of the nicotine patch; (5) current use of nicotine replacement therapy or other smoking cessation medications (e.g., Chantix or Zyban); (6) current enrollment in another smoking cessation program; and (7) blows \leq 5 CO into a breath analyzer at baseline.

Screening: Potential study participants will provide verbal informed consent to complete a phone screening that assesses eligibility. If eligible, participants will attend a baseline session described below. Those who do not screen eligible will be informed and thanked for their time.

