At 12 weeks after the baseline visit, participants will attend a 12-week follow-up visit at the study site. Or if requested, participants can complete a remote study visit, where they will be mailed a CO monitor (by the study team and complete study tasks via video call on Zoom Health with a study team member. Study participants will be asked to report a 7-day point prevalence abstinence of smoking cigarettes and provide a breath sample using Micro _{+TM basic} Smokerlyzer_®. They will also be given a follow-up survey that includes questions asked at baseline and process questions dictated by the primary outcomes that assess the usability and acceptability of Lumme (see Table 1).

At the 12-week follow-up visit, semi-structured in-depth interviews will take place with participants. The in-depth interviews will be approximately 10-30 minutes in length and no additional compensation will be provided. The in-depth interviews will be conducted by the study coordinator and research assistants, the members responsible for conducting follow-up visits. These interviews aim to fill gaps in the literature by taking a qualitative approach to understanding the acceptability of the

Lumme app as a smoking cessation tool in the intervention arm and learn more about all participants' opinions on the recruitment and enrollment process. Both groups will answer questions including: 1) How would you modify the outreach and recruitment process to improve it or make it easier? 2) How comfortable were you with the recruitment, screening and enrollment process? 3) How can we improve the current screening process? Some of the questions the questionnaire will include for the intervention group are: 1) Please describe your general perceptions and expectations of the app, 2) How often did you use the app? 3) How helpful was the app for tobacco cessation?

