The team will adhere to qualitative research processes to ensure the credibility, confirmability, dependability, and transferability of the qualitative data from these analyses.₃₄ To support the credibility of the data, we will conduct peer debriefing and triangulate findings across multiple data sources (surveys). In addition, we will use "member checks," i.e., sharing of initial data interpretations with participants to ensure accurate interpretations. Triangulation of findings, along with reflexivity, will enhance the confirmability of the interpretations. The investigators will carefully record an audit trail and keep extensive field notes to facilitate transferability of study findings into other contexts. At the end of the 12-week follow-up visit, participants will be compensated \$60 for their participants will also receive a Metrocard at each in-person visit.

Operationalization of Outcome Measures: The primary outcome for determining preliminary efficacy will be biochemically validated 7-day point prevalence abstinence.

Analysis: This is a pilot study meant to assess preliminary feasibility, acceptability, and efficacy. Given the small sample size, the purpose of the arms is simply to monitor for unexpected, gross differences between arms.

To determine acceptability, we will ask participants in both arms how useful each of the intervention components are (1 = *Not at all useful* to 7 = *Extremely useful*) and whether they would recommend the program to a friend (1 = *Definitely would not recommend* to 7 = *Definitely would recommend*). For the intervention to be deemed acceptable, the mean level for each of these measures would have to be five or higher.

All in-depth interviews will be transcribed verbatim and then coded. The development and application of a coding scheme is an integral component of the data analysis process. It enables the systematic examination and interpretation of the data related to the primary analytic foci. The coding scheme is conceptualized as a multilevel structure. At the highest level are the primary analytic foci coded as headings. Specific aspects or dimensions of the headings are assigned core codes. Specific aspects or dimensions of the core codes are assigned sub codes. We use ATLAS.ti, a software program for qualitative analysis, to facilitate the analysis.

The following 7 steps will be used to develop the coding scheme:

- Step 1: Identify the principal issues discussed by interviewees.

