- Step 2: Construct definitions of the primary analytic themes.
- Step 3: Develop and apply core codes and sub-codes to the initial set of interviews.
- Step 4: Develop a provisional coding scheme.
- Step 5: Test and refine the provisional coding scheme.

Step 6: Reconcile coding differences and construct an updated and final coding scheme. Step 7: Apply the coding scheme to the full data set and assess inter-coder reliability.

After all transcripts have been coded, we will extract and examine the content of text segments linked to core codes and sub-codes relevant to understanding the technology acceptance of the Lumme app and barriers and facilitators to its use. Based on the coded data, we will propose ways in which certain themes are analytically related. A careful examination of the coded text will reveal the associations among these themes, and may lead to more refined data searches. Once we establish patterns of relationships among themes and issues, we will identify participants' accounts that support or refute these patterns. Identifying and accounting for cases that deviate from an interpretative pattern enable us to test and confirm the pattern's validity and robustness. [name] has done extensive work understanding technology acceptance with particular emphasis on end-users' needs. ³⁵⁻³⁸

Efficacy of the intervention will be based on self-reported 7-day point prevalence abstinence at the follow-up survey. Lost-to-follow-up participants will be included as smokers. The abstinence rate will be calculated.

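### The primary outcome is CO-validated abstinence, but the efficacy analysis uses self-reported abstinence, so the planned analysis does not estimate the stated outcome

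*Combined protocol and SAP*

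**What the plan says.** The section Operationalization of Outcome Measures states: "The primary outcome for determining preliminary efficacy will be biochemically validated 7-day point prevalence abstinence". It is the only place that names a primary efficacy outcome.

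The last paragraph of the Analysis section, just before the references, is the only text on the efficacy analysis: "Efficacy of the intervention will be based on self-reported 7-day point prevalence abstinence at the follow-up survey". It then adds "Lost-to-follow-up participants will be included as smokers" and "The abstinence rate will be calculated".

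The data for a validated outcome are planned. For the 12-week visit the protocol says "Study participants will be asked to report a 7-day point prevalence abstinence of smoking cigarettes and provide a breath sample", and participants who choose a remote visit are mailed a CO monitor. Table 1 lists CO concentration and 7-day abstinence at baseline and 12 weeks.

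The only CO limit in the document is for entry. Under Study Populations, participants must "blow >5 CO into a breath analyzer at baseline", and those at or below 5 are excluded. The Procedures section gives the unit as ppm. No limit is stated for confirming abstinence at 12 weeks.

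**The concern.** The outcome definition and the analysis rule name different variables, and nothing in the text reconciles them. An analyst who follows the definition and one who follows the analysis paragraph could report different efficacy results from the same data. The choice between them stays open until the data have been seen.

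The Background makes the gap more awkward. It lists among the limitations of earlier studies in this population "lack of randomization, comparison conditions, treatment fidelity assessments, abstinence verification tests". This trial does carry out a verification test, but the written analysis makes no use of it.

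Reporting could also differ by arm. Participants know whether they were given a smartwatch and app. Only the Lumme arm has smoking detected by a device, and the study coordinator, who helps conduct the follow-up visits, can view Lumme data on a dashboard (described as anonymized). Over-claiming of abstinence might therefore not be equal between arms, in which case self-report would distort the arm difference as well as the level.

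**Working it through.** The plan contains no quit rate, effect size, alpha or power, so there is no figure to reproduce. The check is a comparison of the two rules, followed by an illustration of scale.

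**How each rule classifies a participant at 12 weeks** (taking validated to mean self-report confirmed by CO)

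| 12-week data | Outcome as defined | Analysis as written |
|---|---|---|
| Reports smoking | Smoker | Smoker |
| Reports abstinence, CO low | Quit | Quit |
| Reports abstinence, CO raised | Not a validated quit | Quit |
| Reports abstinence, no CO reading | Not a validated quit | Quit |
| Lost to follow-up | Not a validated quit | Smoker |

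The rules disagree in the third and fourth rows. Validated quits are a subset of self-reported quits, so the self-reported rate can only equal or exceed the validated one. Telling a low reading from a raised one also needs a 12-week limit, which the plan lacks.

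**Inputs from the protocol.** 40 participants (Study Design), randomized 1:1 (Procedures): 40/2 = 20 per arm. One person is 1/20 = 5 percentage points.

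**Assumptions.** s is the self-reported rate in an arm and f the share of self-reported quits that fail validation. Neither is in the documents.

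**Level.** Expected validated rate = s × (1 − f), with f from 10% to 40%:
- s = 40% (8/20): 0.40 × 0.60 = 24% to 0.40 × 0.90 = 36%.
- s = 30% (6/20): 0.30 × 0.60 = 18% to 0.30 × 0.90 = 27%.

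These are expected values. In whole people, 8/20 (40%) becomes 7/20 = 35%, 6/20 = 30% or 5/20 = 25% if 1, 2 or 3 fail.

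**Arm difference.** Suppose both arms self-report 40%:
- With f = 10% in one arm and 30% in the other, the expected validated rates are 0.40 × 0.90 = 36% and 0.40 × 0.70 = 28%. That is an 8-point difference which self-report shows as zero.
- In whole people, one failure against three gives 35% and 25%, a 10-point difference.

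Conversely, suppose the validated rate is 20% in both arms, so that s = 0.20/(1 − f):
- f = 25% against 10%: 26.7% against 22.2%, a false difference of 4.4 points.
- f = 50% against 10%: 40.0% against 22.2%, a false difference of 17.8 points.
- f equal in both arms: no false difference.

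**Precision for comparison.** The 95% half-width for a difference at 20 per arm is 1.96 × √(2p(1 − p)/20): 24.8 points at p = 20% and 28.4 points at p = 30%.

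**The case against.** The strongest reply is that the analysis sentence is only loosely worded. It does not call its variable primary and does not rule out validation. Self-report and breath sample are taken at the same visit, so the sentence could be naming the self-report half of a validated measure. But the sentence cites the survey as its source, and the only default to smoker is for people lost to follow-up. Nothing in it makes a raised or missing CO reading count against a claimed quit.

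The second reply is that little depends on it. The Analysis section says the arms serve only to watch for gross differences, no test is planned, and the 8-point example lies well inside a half-width of about 25 to 28 points. This stands as a limit on the consequences for the arm comparison. It does not settle which variable is reported, and the level of abstinence is affected whatever the arms show.

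Several narrower points also stand:
- Remote visits are not unverified by design; a reading may simply be missing or discordant.
- The two rules give different results only if at least one participant is discordant or lacks a reading.
- Different over-claiming by arm is plausible but not shown, and its direction is unknown. If device tracking deters over-claiming, self-report would work against Lumme.
- The 5 ppm limit is stated for entry only, so using it at 12 weeks is a proposal that the investigators should confirm.

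**Conclusion.** The concern holds, and the text must be fixed. The analysis rule is wrong as written for the stated primary outcome: it counts as quits people whom the outcome definition would not. This conclusion rests on the current text alone and needs no assumed rate.

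The size does rest on assumptions. Across the assumed 10-40% failure range, an arm's rate would be overstated by 4 to 16 points at a self-reported 40% (40 − 36 and 40 − 24) and by 3 to 12 points at 30% (30 − 27 and 30 − 18). Bias in the arm difference arises only if failure shares differ between arms, and the documents cannot give its size or sign. The defect lies in the analysis text, not in data collection, so it can be fully repaired.

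**What to change.** Replace the analysis sentence with text along these lines:

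> Efficacy will be assessed by biochemically validated 7-day point prevalence abstinence at 12 weeks, defined as a self-report of no smoking in the past 7 days together with exhaled CO of 5 ppm or less. Anyone lost to follow-up, or reporting abstinence without a valid breath sample, is counted as a smoker.

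The 5 ppm limit is the one the trial already uses at entry. If the investigators prefer another, they should justify it and fix it before 12-week data are examined. Counting a missing reading as smoking extends the plan's existing rule for loss to follow-up.

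Report self-reported abstinence as a secondary outcome. Show by arm how many self-reported abstainers had CO above the limit and how many had no reading, so that any difference in over-claiming is visible.

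The cost is a few lines of text and no new data collection. The reported abstinence rate may be lower than under self-report, by an amount the documents do not allow one to predict.
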